#### **15.2.4 Sensitivity analyses**

In the event of discrepancies for the stratification factors between the IRT system and the eCRF, the analysis described in Section 15.2.3 will be repeated using the stratification factors as entered in the eCRF and considered as a sensitivity analysis of the main analysis.

The robustness of inferences from the primary endpoint analysis to deviations from its underlying modelling assumptions will be explored using several sensitivity analyses. Table 11 gives an overview of the planned sensitivity analyses that are described in this section.

**Table 11 Summary of sensitivity analyses for missing data**

Section	Variable	Imputation method	Analysis	Comment/purpose
15.2.3	Change from baseline to M6	MI (CR)	ANCOVA	Main analysis: MAR model in placebo arm, MNAR (CR) in lucerastat arm
15.2.4	Change from baseline to M6	MI (CR)	ANCOVA	Using the stratification factors as entered in the eCRF
15.2.4.1	Change from baseline to M6	MI (MAR)	ANCOVA	Imputation: MAR model Impact of departures from MNAR/CR assumptions
15.2.4.2	Change from baseline to M6	MI (J2R)	ANCOVA	Imputation: MAR model in placebo arm, MNAR (J2R) in lucerastat arm Impact of departures from MNAR/CR assumptions

M6: Month 6.

ANCOVA = Analysis of covariance; CR = copy reference; eCRF = electronic case report form; J2R = jump to reference, MAR = missing at random; MI = multiple imputation; MNAR = missing not at random.

#### 15.2.4.1 Model-based analysis relying on the MAR assumptions

Missing monthly modified BPI-SF3 scores will be imputed using a MI method [Rubin 1987] based on a model including the baseline modified BPI-SF3 score, stratification factors, all available post-baseline monthly scores up to Month 6, and treatment group. In contrast to the CR approach described in Section 15.2.3, treatment group is included in the imputation model and therefore missing data for subjects from the lucerastat arm will be imputed using data from the lucerastat arm.

The MI procedure will be implemented by the following SAS® code:

```
proc mi data=h nimpute=500 seed=32767 minimum = . . . . 0 0 0 0 0 0 maximum = . . . . 10
10 10 10 10 10 minmaxiter=1000000out=h2;
mcmc impute = monotone;
var treatment sex ertstatus baseline y1 -- y6;
run;
proc mi data=h2 nimpute=1 seed=32767 minimum = . . . . 0 0 0 0 0 0 maximum = . . . . 10
10 10 10 10 10 minmaxiter=1000000out=h3;
by _imputation_;
class treatment sex ertstatus;
var treatment sex ertstatus baseline y1 -- y6;
monotone regression;
run;
```

An ANCOVA model will then be used to analyze this endpoint on each imputed dataset as described in Section 15.2.3.

#### 15.2.4.2 Model-based analysis relying on a different MNAR scenario

Missing monthly modified BPI-SF3 scores will be imputed using a MI assuming MNAR using the Jump to Reference (J2R) approach [Carpenter 2013]. The J2R approach assumes that subjects with missing data in the lucerastat group have outcomes similar to outcomes from the placebo group, starting from the point of monotone missing data. In contrast to CR, for subjects in the lucerastat group, non-missing earlier values are ignored in the prediction of later missing values. Therefore, the treatment difference from the lucerastat group in subjects with missing data disappears immediately after the point where missing data occurs.

The MI procedure will be implemented by the following SAS® code:

```
proc mi data=h6 nimpute=1 seed=32767 minimum = . . . . 0 maximum = . . . . 10
minmaxiter=1000000 out=h3;
by _imputation_;
class treatment sex ertstatus;
var sex ertstatus bsl y6;
mnar model (y6 / modelobs=(treatment="placebo"));
monotone regression;
run;
```

An ANCOVA model will then be used to analyze this endpoint on each imputed dataset as described in Section 15.2.3.

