### 15.2.3 Primary statistical analysis

The primary analysis will be performed on the mFAS, according to the intent-to-treat approach. All available data will be used regardless of occurrences of ICEs, such as premature treatment discontinuation or changes in background medication.

The null hypothesis will be tested using the two-sided significance alpha level = 0.05, using the following method.

The observed data cannot be used to distinguish between missing at random (MAR) and missing not at random (MNAR) missing data mechanisms [NRC Report 2010] and in incomplete-data settings a definitive MNAR analysis does not exist [Molenberghs 2004].

An analysis based on a pattern-mixture model will be performed using a MAR imputation in the placebo arm while using a MNAR approach in the lucerastat arm: missing data will be imputed applying a control-based multiple imputation (MI) assuming MNAR using the CR approach [Carpenter 2013]. Instead of imputing a single value for each missing observation, a set of values is generated from the model, resulting in as many distinct complete datasets without missing data. The imputation model includes the baseline value, the two stratification factors (sex and ERT treatment status at screening) and all post-baseline monthly scores up to Month 6. Missing data for subjects from both treatment arms will be imputed using data from the placebo arm. This approach assumes that subjects with missing data in the lucerastat arm have outcomes trending towards outcomes observed in the placebo arm, i.e., the imputations result in a treatment effect that gradually diminishes towards the placebo arm.

More specifically, the imputations will be performed in two steps: “intermittent” missing data (a monthly score is missing but one or more monthly score[s] is [are] available in following month[s]) will be first imputed by a Markov chain Monte Carlo method using a non-informative Jeffreys prior, thus creating 500 partially imputed “monotone” datasets; then, the remaining missing data will be imputed once in each of these 500 “monotone” imputed datasets using the CR approach leading finally to 500 complete imputed datasets. Imputed values will be restricted to remain in the clinically relevant range of [0, 10].

The two-step MI procedure will be implemented by the following SAS® code:

```

proc mi data=h nimpute=500 seed=32767 minimum = . . . . 0 0 0 0 0 0 maximum = . . . . 10
10 10 10 10 10 minmaxiter= 1000000out=h2;

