  mcmc impute = monotone;
  var treatment sex ertstatus baseline y1 -- y6;
run;
proc mi data=h2 nimpute=1 seed=32767 minimum = . . . . 0 0 0 0 0 0 maximum = . . . . 10
10 10 10 10 10 minmaxiter=1000000out=h3;
  by _imputation_;
  class treatment sex ertstatus;
  var sex ertstatus bsl y1 -- y6;
  mnar model (y1 -- y6 / modelobs=(treatment="placebo"));
  monotone regression;
run;

```

An analysis of covariance (ANCOVA) model will then be used to analyze this endpoint on each imputed dataset. The following terms will be included in the model: baseline value, the two stratification factors (sex and ERT treatment status at screening), and the treatment group. This analysis will be implemented by the following SAS® code:

```

proc mixed;
  by _imputation_;
  class sex ertstatus treatment;
  model change = sex ertstatus bsl treatment;
  lsmeans treatment / cl pdiff;
run;

```

Uncertainty in the imputations will be reflected appropriately in the analysis by combining the results on each imputed dataset using Rubin's methodology [Rubin 1987]. The final estimate is the mean of the 500 per-imputation estimates and the final variance is the sum of the average within-imputation variance and  $(1 + 1 / 500)$  times the between-imputation variance [Rubin 1987]. From the final point estimate and variance, the 95% CI will be determined.

The results aggregation of the MI procedure after analysis of the 500 complete datasets will be implemented by the following SAS® code:

```

proc mianalyze data = <ods output lsmeans from proc mixed>;
  ods output parameterestimates=ls_m_comb;
  by treatment;
  modeleffects estimate;
  stderr stderr;
run;

proc mianalyze data = <ods output diffs from proc mixed>;
  ods output parameterestimates=diff_comb;
  modeleffects estimate;
  stderr stderr;
run;

```

The mean difference in changes from baseline to Month 6 between lucerastat and placebo together with its two-sided 95% CI and p-value will be reported.

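### Two PROC MI calls carry one bounds entry too many; read by position, the jump-to-reference call leaves Month 6 outside the stated 0 to 10 limit

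*SAP*

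**What the plan says.** SAP 15.2.3 fixes the range for the primary analysis: "Imputed values will be restricted to remain in the clinically relevant range of [0, 10" (the scale limits). It then prints a two-step PROC MI procedure as the implementation. The first step fills intermittent gaps to give 500 monotone datasets. The second step applies CR and begins "proc mi data=h2 nimpute=1 seed=32767 minimum = . . . . 0 0 0 0 0 0 maximum = . . . . 10", with the variable list "var sex ertstatus bsl y1 -- y6".

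SAP 15.2.4.2 describes J2R as a sensitivity analysis and prints one call. It begins "proc mi data=h6 nimpute=1 seed=32767 minimum = . . . . 0 maximum = . . . . 10" and has the variable list "var sex ertstatus bsl y6". On earlier values the text says that "for subjects in the lucerastat group, non-missing earlier values are ignored in the prediction of later missing values".

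Table 11 labels J2R "Imputation: MAR model in placebo arm, MNAR (J2R) in lucerastat arm" and the primary analysis "Main analysis: MAR model in placebo arm, MNAR (CR) in lucerastat arm". SAP 15.3.1 reuses both approaches for abdominal pain.

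**The concern.** The bounds in PROC MI are given as a list alongside the variables, and the SAP's other calls are laid out so that entry and variable match one for one. In the two calls that model on placebo only, treatment is no longer in VAR, but the lists were not shortened. The zeros and tens then no longer sit opposite the scores they are meant to limit.

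The code is presented as the implementation, with the seed and number of imputations fixed, so a programmer may copy it as it stands. At stake is whether the J2R sensitivity analysis respects the 0 to 10 scale at Month 6, the only score it imputes, and whether the primary analysis call is affected.

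**Working it through.** **Count of entries against variables** (`y1 -- y6` counts as six):

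| Call | Bounds entries | VAR variables |
|---|---|---|
| 15.2.3 CR, step 1 | 10 | 10 |
| 15.2.3 CR, step 2 | 10 | 9 |
| 15.2.4.1 MAR, step 1 | 10 | 10 |
| 15.2.4.1 MAR, step 2 | 10 | 10 |
| 15.2.4.2 J2R | 5 | 4 |
| 15.3.3 Gb3, step 1 | 8 | 8 |
| 15.3.3 Gb3, step 2 | 8 | 8 |

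Five of the seven printed calls match. The two that do not are the two without treatment in VAR.

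**Pairing by position**

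- J2R: sex, ertstatus, bsl and y6 each take a dot. The 0 and the 10 are left over, so y6 has no limit.
- CR step 2: sex, ertstatus, bsl and y1 take dots, and y2 to y6 take 0 and 10. One 0 and one 10 are left over, so only y1 has no limit.

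**Who is affected in CR step 2.** Step 1, with correct 10/10 bounds, makes each record monotone. After that, y1 can be missing only if y1 to y6 are all missing, that is, for a subject with no monthly score. For such a subject y1 is drawn without limits, but y2 to y6, including the analysed Month 6 value, stay within 0 to 10.

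**How often an unbounded draw leaves the scale.** For a normal draw with mean m and SD s, P(outside) = Φ((0 - m)/s) + 1 - Φ((10 - m)/s). With m = 6 and s = 3 this is Φ(-2.00) + 1 - Φ(1.33) = 0.023 + 0.091 = 11.4%. Over m = 4 to 7 it is 0.1% to 2.3% at s = 1.5 and 10% to 17% at s = 3. These m and s are assumed.

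**Effect on the J2R difference (simulation)**

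- From Protocol 10.5: placebo change +0.75 and lucerastat change -1.25 (midpoints of the stated ranges), SD of change 3.
- Assumed, not in the documents: baseline mean 6; Month 5 to 6 correlation 0.70 to 0.90; 5% to 20% missing per arm; odds of dropout multiplied by 1 to 2 per pain point.
- Method: 60,000 subjects per arm, scores kept on 0 to 10. Month 6 is regressed on baseline in observed placebo, and the draws are applied to missing values in both arms, once unbounded and once bounded. ANCOVA on baseline follows. The strata and the baseline entry threshold of 4 were not simulated.
- Result: 8.2% to 23.0% of unbounded draws fall outside 0 to 10. Unbounded minus bounded difference: at most 0.011 points with equal missingness, and -0.066 to +0.092 points at 10% versus 20%.

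The near-zero result arises because one model serves both arms, so the shift cancels when equal fractions are imputed. That cancellation depends on the call imputing both arms. If placebo is already complete in h6, the unbounded draws fall on lucerastat only. A rough upper figure then follows from the result above: 0.092/0.10 = 0.92 points per imputed value, so 0.92 x 0.05 = 0.05, 0.92 x 0.10 = 0.09 and 0.92 x 0.20 = 0.18 points at 5%, 10% and 20% missing. The direction would be toward no effect, because the assumed placebo mean of 6 + 0.75 = 6.75 lies nearer to 10 than to 0.

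For scale, with about 79 and 39 subjects (SAP 2) and SD 3, the unadjusted standard error is 3 x sqrt(1/79 + 1/39) = 0.59.

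**The case against.** The best defence is that this is a typing slip whose intent is plain: SAP 15.2.3 states the range in words, and the J2R call itself carries a 0 and a 10. If SAS refuses an over-long list, the programmer sees an error and deletes a dot before any result exists. J2R is a sensitivity analysis outside the testing sequence, and the diary continues after treatment stops, which limits missing data. All of this stands and is why the point is minor. It does not remove the mismatch: neither way of handling the surplus entry gives the stated limit from the code as printed.

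Two stronger readings are tempting.

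- **That the primary result is compromised.** The documents do not support this. Read by position, Month 6 stays bounded in CR step 2, and the loosened Month 1 limit touches only subjects with no monthly score. If the call is rejected, no wrong result is produced.
- **That J2R imputes placebo subjects without their earlier scores.** The call omits y1 to y5 for both arms and reads h6, which no printed step creates. But it runs by imputation number with one imputation each, so it is visibly the last step of a longer procedure. If h6 already holds completed placebo values, the code agrees with the text. The Table 11 label lists no covariates, and a model on sex, ERT status and baseline is also a MAR model. This is missing detail, not a demonstrated error.

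**Conclusion.** The bounds lists are wrong as printed in two calls, and read by position the J2R call does not hold Month 6 to 0 to 10. The count is certain. How SAS treats the surplus entry was not tested.

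The expected effect on the J2R difference is small: about 0.01 points or less with equal missingness and about -0.07 to +0.09 points at 10% versus 20%, if the call imputes both arms. It is somewhat larger, but still a fraction of the standard error, if the call imputes lucerastat alone. These sizes rest on assumed baseline level, correlations, missingness and dropout pattern. The primary estimand, alpha and power do not change. Severity: minor.

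**What to change.** - In SAP 15.2.4.2, set the J2R bounds to `minimum = . . . 0 maximum = . . . 10`. This pairs four entries with four variables, and y6 takes 0 and 10.
- In SAP 15.2.3, CR step 2, use three dots followed by six 0s for the minimum and three dots followed by six 10s for the maximum. This pairs nine with nine, and y1 to y6 are all limited.
- Carry the corrected lists over to abdominal pain (SAP 15.3.1), which uses the same approach.
- As a documentation note, state how h6 is created, so that a reader can confirm that placebo Month 6 values are imputed using earlier monthly scores. If that is already done, printing the step is enough.

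The cost is one dot removed from each of four lists and one short addition to the SAP. No model, estimand or test changes.

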### 15.2.5 Supportive analyses

A series of additional analyses based on the modified BPI-SF3 score data are presented below and will support the primary endpoint results by analyzing the primary endpoint variable using various methods and assumptions.

Table 12 below gives an overview of the planned supportive analyses that are described in this section.

**Table 12 Summary of supportive analyses**

Section	Variable	Imputation method	Analysis	Comment/purpose
15.2.3	Change from baseline to M6	MI (CR)	ANCOVA	Main analysis: MAR model in placebo arm, MNAR (copy reference) in lucerastat arm
15.2.5.1	Responder at M6	Missing = NR (SI)	CMH	Responder if score reduction from baseline at least 30% Missing at M6 = non-responder
15.2.5.2	Change from baseline to M6	MI (CR)	ANCOVA	Impact of not being treated (analysis on FAS)
15.2.5.3	Change from baseline to M6	MI (CR)	ANCOVA	Impact of protocol deviations (analysis on PPS)
15.2.5.4	Change from baseline to M6	MI (CR)	ANCOVA	Impact of use of significant rescue pain therapy Daily scores on days with use of any significant rescue pain therapy substituted by the worst score of subject during the double-blind treatment period
15.2.5.5	Change from baseline to M1, M2, ..., M6	None	MMRM	Mean score by treatment at each month Difference between treatment means at each month Characterization of response over time
15.2.5.6	Responder at M6 if x% reduction	Missing = NR (SI)	CMH	Impact of cut-off for responder definition: responder if score reduction from baseline at least x% (x = 20, 40, 50) instead of 30%
15.2.5.7	Percentage of subjects achieving a x% reduction at Month 6	Missing = NR SI)	Descriptive	Cumulative responder analysis in graph form
15.2.5.8	Improvement according to PGIC (PGIC-DS, PGIC-PS) at Month 6 visit	None	Description, ROC curve	Provides support for clinical relevance of the primary endpoint Using PGIC at Month 6 as an anchor, determines what would be the best cut-off on modified BPI-SF3 change (absolute change or percent change) based on data observed in the study population.
15.2.5.9	Improvement according to	None	Description, ROC curve	Provides support for clinical relevance of the primary endpoint

Section	Variable	Imputation method	Analysis	Comment/purpose
	change in PGIS-D (or PGIS-P) at Month 6 visit			Using change in PGIS-D at Month 6 as an anchor, determines what would be the best cut-off on modified BPI-SF3 change (absolute change or percent change) based on data observed in the study population. Same approach applied separately for change in PGIS-P.
15.2.5.10	Change from baseline to M6	None	Descriptive	Investigates associations between change in neuropathic pain and changes in other FD manifestations (abdominal pain, diarrhea). Scatter plots by treatment group of change in modified BPI-SF3 score vs change in the considered symptom, Spearman correlation coefficients.

M1, M2, ..., M6: Month 1, 2, 3, 4, 5, 6.

ANCOVA = Analysis of covariance; BPI-SF3 = Brief Pain Inventory-Short Form item 3; CMH = Cochran-Mantel-Haenszel test; CR = Copy Reference; FAS = Full analysis set; FD = Fabry disease; MAR = Missing at random; MI = multiple imputation; MNAR = Missing not at random; MMRM = mixed model for repeated measures; NR = non-responder; PGIC = Patient Global Impression of Change; PGIC-DS = Patient Global Impression of Change in Disease Severity; PGIC-PS = Patient Global Impression of Change in neuropathic Pain Severity; PGIS-D = Patient Global Impression of Severity of Disease; PGIS-P = Patient Global Impression of Severity of neuropathic Pain; PPS = Per-protocol analysis set; ROC = receiver operating characteristic; SI = single imputation.

### 15.2.5.1 Responder analysis

A cut-off of 30% in pain reduction was selected for this responder analysis because this 30% reduction in pain has been shown to represent important improvement in patients with neuropathic pain [Farrar 2001] and it is recommended that the percentages of patients responding with this degree of pain relief be reported in clinical trials of chronic pain treatments [Dworkin 2008]. Based on the evidence found in the literature in non-Fabry patients with neuropathic pain and regulatory guidelines [EMA 2007] (later replaced by [EMA 2017]), a cut-off of 30% was selected.

Using subject responses from the modified BPI-SF3, a response variable (yes/no) for the primary endpoint will be calculated based on a reduction of at least 30% from baseline to Month 6 in the modified BPI-SF3 score of “neuropathic pain at its worst in the last 24 hours”.

Subjects who have a missing modified BPI-SF3 score at Month 6, for any reason, will be considered as non-responders, i.e., the worst possible outcome is assumed.

The Cochran-Mantel-Haenszel (CMH) test stratified by sex and ERT treatment status at screening (treated vs not treated) will be used to test for a difference in the proportions of responders at Month 6 between treatment groups.

The treatment effect (lucerastat vs placebo) will be expressed in terms of the common odds ratio (ORc) and corresponding 95% CI. An  $ORc > 1$  will indicate a response to treatment in favor of lucerastat as compared to placebo.

Homogeneity of the treatment effect across strata will be investigated using the Breslow-Day test.

This analysis will be implemented by the following SAS® code:

```
proc freq;
  tables sex*ertstatus*treatment*response / nocol nopercnt cmhl
  commonriskdiff (cl=newcombe);
run;
```

The Mantel-Haenszel risk (proportion) difference (lucerastat vs placebo) and corresponding 95% CI (stratified by sex and ERT treatment status at screening) will also be provided. The CIs are calculated using the stratified Newcombe method [Yan 2010].

#### ***15.2.5.2 Change from baseline to Month 6 on the FAS***

If the FAS and mFAS differ by at least 5 subjects, an analysis on the FAS will be performed in order to assess the impact of not taking the study treatment. This analysis will be conducted as the main analysis.

#### ***15.2.5.3 Change from baseline to Month 6 on the PPS***

An analysis on the PPS will be performed in order to assess the impact of protocol deviations on the assessment of the primary endpoint. This analysis will specifically address the issue of the lack of adherence to protocol or compliance with study medication until the intended EOS.

#### ***15.2.5.4 Change from baseline to Month 6 where data on days with use of any significant rescue pain therapy are substituted by a worst score***

The modified BPI-SF3 scores of “neuropathic pain at its worst in the last 24 hours” on the days that a subject received any significant rescue pain therapy are substituted by the worst score of that subject during the double-blind treatment period. Monthly scores are then derived as described in Section 9.1 and the same analysis model as described in Section 15.2.3 will be applied.

